3.2 Study Duration, Enrollment and Number of Sites

This study will be conducted at 5 investigative clinic sites; West Penn Hospital, Forbes Regional Hospital, Jefferson Regional Hospital, Bethel Park Surgery Center, and Monroeville Surgery. Recruitment will stop when a minimum of 230 subjects are consented. The duration of the study for an individual patient will be two years from the surgery date. This will include the pre-operative assessment, surgery, regular post-operative appointments and a final two year follow-up, as noted in the table in the schedule of study section.

3.2.1 Duration of Study Participation

The study duration will require 7 visits to the clinic plus a surgery day therefore will require a pre-surgical visit/screening, surgery procedural day and six outpatient post-operative visits to the clinics. The entire follow up period will occur over 2 years.

3.2.2 Total Number of Study Sites/Total Number of Subjects Projected

The study will be conducted at 5 AHN investigative sites in the United States; West Penn Hospital, Jefferson Regional Hospital, Forbes Regional Hospital, Bethel Park Surgery Center, and Monroeville Surgery Center. Recruitment will stop when at least 115 subjects are randomly included in each of the two study arms. It is expected that approximately 230 subjects will be enrolled.

3.3 Study Population

3.3.1 Inclusion Criteria

- 1) Males or females age 18 to 89 years
- 2) Undergoing foot and ankle surgery
- 3) Must be able to read and understand English and consent for themselves

3.3.2 Exclusion Criteria

- 1) Diagnosed peripheral neuropathy
- 2) Diagnosed peripheral vascular disease
- 3) Documented infection to the surgical extremity
- 4) Previous surgery to the surgical limb

- 5) Laboratory abnormalities that indicate clinically significant hematologic, hepatobiliary, or renal disease which would predispose patients to poor healing and/or non-union
- 6) Subjects who, in the opinion of the Investigator, may be non-compliant with study schedules or procedures.

Subjects that do not meet all of the enrollment criteria may not be enrolled. Any violations of these criteria must be reported in accordance with IRB Policies and Procedures.

4 STUDY PROCEDURES

4.1 Screening Visit

Below is a list of all of the procedures to be performed at each visit.

- Informed Consent
- Physical Exam
- Radiographic/Advanced Imaging
- Medical Record Review
 - Review of the medical record will include reviewing the past medical and surgical history, laboratory values, and most recent visits to other health care providers in the standard fashion of any office or inpatient encounter
- Surgical procedure discussed and operative consent
- Pre-operative AOFAS and SF-36 surveys completed

4.2 Surgical Visit

4.2.1 Surgery

- Physical Exam
- Medical Record Review Necessary surgical procedure performed

4.3 Follow-up Phase

Follow-up Visit 1 (2-3 weeks post-op)

- Physical Exam
- Radiographic/Advanced Imagining
- Sutures removed
- Medical Record Review

Follow-up Visit 2 (6-8 weeks post-op)

- Physical Exam
- Radiographic/Advanced Imagining
- Post-op AOFAS and SF-36 survey
- Medical Record Review

Follow-up Visit 3 (3 months post-op)

- Physical Exam
- Radiographic/Advanced Imagining
- Post-op AOFAS and SF-36 survey
- Medical Record Review

Follow-up Visit 3 (6 months post-op)

- Physical Exam
- Radiographic/Advanced Imagining
- Medical Record Review

Follow-up Visit 4 (12 months post-op)

- Physical Exam
- Radiographic/Advanced Imagining
- Post-op AOFAS and SF-36 survey
- Medical Record Review

Follow-up Visit 5 (24 months post-op)

- Physical Exam
- Radiographic/Advanced Imagining
- Post-op AOFAS and SF-36 survey
- Medical Record Review

4.4 Unscheduled Visits

Unscheduled visits necessary to address any post-operative complications will be included in the patients study record. At no time will the welfare of the patient be compromised for the execution of the study. If at any time it is decided that a patient should be withdrawn from one of the two study arms, it will be recorded in the study results.

4.5 Subject Completion/Withdrawal

Subjects may withdraw from the study at any time without prejudice to their care. They may also be discontinued from the study at the discretion of the Investigator for lack of adherence to study treatment or visit schedules, or AEs. The Investigator may also withdraw subjects who violate the study plan, or to protect the subject for reasons of safety or for administrative reasons. It will be documented whether or not each subject completes the clinical study

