The subjects will be identified/recruited during clinic hours as patients requiring an elective or traumatic foot and ankle surgery. During the clinic hours the primary investigator and/or the co-investigator will obtain full consent from the patient. We will recruit a minimum of 115 participants into each of two study arms, an immediate weight-bearing arm and a non-weight-bearing arm, so 230 participants will be included. Patients will be eligible if they are undergoing elective or traumatic foot and ankle surgery. Exclusion criteria will include any patient less than 18 years of age & over 89, history of foot or ankle surgery on the surgical limb, any degree of diagnosed peripheral neuropathy or peripheral vascular disease, infection, and/or unwillingness to participate at random in one of the two study arms.

Study Interventions and Measures:

We will be assessing the difference in two groups; immediate protected weight-bearing in a CAM walking boot vs strict non-weight-bearing for 6 weeks following foot and ankle surgery. Monitoring will be done by way of clinical follow-up, serial radiographs and/or other appropriate imaging modalities, and patient reported outcomes by way of AOFAS and SF-36 surveys.

Surgical procedures performed on patients included in the study will vary, as will the outcome measures for each procedure. Osseous fusions, including both elective joint fusions and bone healing following trauma, will be assessed by both clinical and radiographic evaluation. Soft tissue procedures, including elective stabilization and traumatic soft tissue repairs, will be assessed clinically and with imaging modalities

deemed appropriate. Complications during the perioperative and post-operative periods, such as non-union, infection, etc. will be included in the outcomes. All participants will also complete AOFAS and SF-36 surveys in the pre-operative and post-operative periods. We will also include return to work, activity, sport, etc. where appropriate.

Study Phase	Screening	Surgery	Post-op 2-3 w	Post-op 6-8 w	Post-op 3 m	Post-op 6 m	Post-op 1 yr	Post-op 2 yr	Unscheduled Visits
Visit Number	1		2	3	4	5	6	7	
Informed									
Informed Consent/Assent	x								
Review Inclusion/Exclusion									
Criteria	х								
Randomization	x								
Demographics/PMH	x								
Physical Examination	x		x	x	x	x	x	x	x
Adverse Event Assessment			x	x	x	x	x	x	x
Radiographs/Imagining	х		x	x	x	x	x	x	x
Complete AOFAS/SF- 36 survey	x			x	x		x	x	

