3 INVESTIGATIONAL PLAN

3.1 General Schema of Study Design

The study will be a randomized 1:1, controlled trial, prospective in nature, where participants undergoing foot and ankle surgery will be randomly placed into one of two

groups; an immediate weight-bearing group or a non-weight-bearing group. The patients will be randomly placed into the study group and control group if they meet all eligibility criteria. The first patient recruited will be assigned a unique study identifier (i.e., FAI001) and a coin flip will randomize the patient into either the study group (Heads) or control group (Tails). From that point, all patients will be placed into their groups by alternating between the control group and the study group. No bias will be placed on the subject or the procedure in regard to inclusion into a certain research group. Patients will be recruited and should they agree will be consented to the study with two year follow up results.

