4.5.1 Early Termination Study Visit

Subjects who withdraw from the study before the 12 month follow-up visit will not be included in the final analysis of the study.

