6.10.1 Follow-up report

If an SAE has not resolved at the time of the initial report and new information arises that changes the investigator's assessment of the event, a follow-up report including all relevant new or reassessed information (e.g., concomitant medication, medical history) should be submitted to the IRB. The investigator is responsible for ensuring that all SAE are followed until either resolved or stable.

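### Section 4.5 lets the investigator end a subject's participation in the study, not only the assigned regimen, and no available section requires later AOFAS/SF-36 surveys or scheduled healing assessments

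*Combined protocol and SAP*

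**What the plan says.** Section 4.5 gives the investigator two sets of grounds for ending participation. A subject may be "discontinued from the study at the discretion of the Investigator for lack of adherence to study treatment or visit schedules, or AEs". It continues: "The Investigator may also withdraw subjects who violate the study plan, or to protect the subject for reasons of safety or for administrative reasons". After that, the section asks only that completion or non-completion be documented.

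Section 4.4 uses a different expression: "If at any time it is decided that a patient should be withdrawn from one of the two study arms, it will be recorded". It does not say whether follow-up continues for such a patient. The same section does place unscheduled visits for complications in the study record.

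Section 4.5.1 is headed as an early termination visit but lists no assessments. Its only content is an analysis rule: "Subjects who withdraw from the study before the 12 month follow-up visit will not be included in the final analysis of the study". Table 1 and section 4.3 have no early-termination visit and no rule for discontinued subjects.

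Two duties concern events. Section 6.8 requires every adverse event, serious or not, to be noted with its duration and outcome. Section 6.10.1 adds, for serious events: "The investigator is responsible for ensuring that all SAE are followed until either resolved or stable". Neither mentions the surveys or the scheduled healing assessments.

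**The concern.** Stopping a regimen and leaving a study are different events. Ordinarily a patient who abandons the assigned regimen, or is taken off it for safety, still attends the planned visits and still contributes outcomes. Section 4.5 allows the investigator to end both at once.

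Three features make this more than a drafting matter.

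- **The reasons for stopping relate to outcome.** Section 6.8 lists wound complications, non-union and delayed soft-tissue healing as risks of the study arm. Section 6.2 makes complications and healing the secondary endpoints. A patient stopped for such an event is unlikely to be typical of the arm.
- **The decision-maker can know the arm.** After a first coin flip, section 3.1 says: "From that point, all patients will be placed into their groups by alternating between the control group and the study group". The abstract describes visibly different regimens: "immediate protected weight-bearing in a CAM walking boot vs strict non-weight-bearing for 6 weeks following foot and ankle surgery". No blinding is described.
- **The reasons may differ between arms.** Section 7.3.4 allows for a minimal increase in complications with weight-bearing, while the control arm has a strict restriction to breach. Equal numbers stopped would not by themselves make the remaining patients comparable.

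At stake are the later primary scores. Section 7.5 names the questionnaires as the exception to standard care, so a survey that is not given will generally not turn up elsewhere.

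**Working it through.** **1. The plan's own figure.** Section 6.5 uses d = 0.40, two-sided alpha 0.05 and 100 evaluable patients per arm for 80% power. The exact t-test solution is 99.08 per arm, rounded up to 100, and power at 100 per arm is 80.4%. The stated size reproduces. The allowance for loss is 15/115 = 13.0% per arm.

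**2. Surveys at risk.** Table 1 and section 4.3 place the surveys at screening, 6-8 weeks, 3 months, 12 months and 24 months. That is five occasions, which agrees with section 7.5, and four of them are post-operative. If collection ends with participation:

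| Stop occurs | Post-operative surveys lost |
|---|---|
| before the 6-8 week visit | 4 of 4 |
| after it, before 3 months | 3 of 4 |
| after 3 months, before 12 months | 2 of 4 |
| after 12 months, before 24 months | 1 of 4 |

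A patient in the first row has no post-operative value on either primary measure.

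**3. Effect on the arm comparison.** In one arm, let w be the share discontinued. Let g be how far, in SD units, their mean would lie below the mean m of those followed. The full-arm mean is (1 - w)m + w(m - g) = m - gw, so the followed patients overstate the arm by gw. For weight-bearing (WB) minus control (C):

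bias = g_WB × w_WB - g_C × w_C

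The documents give neither w nor g, so all inputs here are assumptions:

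- Mild case, 10% versus 5% stopped, g = 0.5 in both arms: 0.5 × 0.10 - 0.5 × 0.05 = 0.025 SD, and 0.025/0.40 = 6% of the design effect.
- Equal shares, unequal reasons, 10% in each arm, g = 1.0 versus 0.25: 1.0 × 0.10 - 0.25 × 0.10 = 0.075 SD, and 0.075/0.40 = 19%.
- Equal shares, equal deficits, 10% in each arm, g = 0.5 in both: 0.5 × 0.10 - 0.5 × 0.10 = 0.

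Exchanging the arms reverses the sign, so the formula gives no direction.

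**4. Power.** Ten per cent of 115 is 11.5 patients per arm, which is below the allowance of 15. Stops on this scale could be absorbed if other losses are small. The allowance protects precision; it does not make those who remain comparable.

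**The case against.** The best case for the plan has five parts.

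- **Complication data are better protected than section 4.5 alone suggests.** The triggering event has already been seen and must be recorded with its outcome (6.8). Complication visits enter the record (4.4), and Table 1 gives them an examination, adverse event assessment and imaging. None of this text expressly reaches the period after discontinuation, but it narrows the gap. This stands.
- **Later healing may be charted.** Visits, examinations and radiographs are standard care (7.5) and are recorded in the electronic record (7.1.2). Some AOFAS items, such as gait and sagittal motion, are examination findings. This stands in part: nothing requires the study to collect these data after discontinuation, and they do not supply an SF-36 or a complete AOFAS score.
- **The clause is permissive and partly protects patients.** Nothing shows that it would be used often or differently by arm. The consent pages are not available and may contain terms on data after withdrawal. This stands, and it limits confidence.
- **The heading of 4.5.1 suggests that an exit visit was intended.** Perhaps so, but no assessment is listed, and one exit visit would not replace the later surveys.
- **The problem is really the exclusion in 4.5.1.** This does not stand. That rule decides who is analysed; section 4.5 decides whether data exist. Removing 4.5.1 would not restore surveys never given, and it does not reach stops between 12 and 24 months.

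A reader might infer that complications of discontinued patients disappear from the safety comparison. Section 4.5 does not do that. It could happen only through 4.5.1, whose wording leaves open whether investigator withdrawals are covered, and it is not claimed here.

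A reader might also take a much larger bias from the same formula: 1.0 × 0.15 - 0.25 × 0.05 = 0.1375 SD, or 34% of 0.40. That needs opposite assumed extremes in the two arms, and 15% stopped in one arm would alone exceed the plan's 13.0% allowance for all losses.

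**Conclusion.** The point holds in a limited form. Section 4.5 permits an investigator who can know the arm to end study participation for adverse events, non-adherence, missed visits or plan violations. No available section then requires the remaining surveys or scheduled healing assessments. The loss falls mainly on later AOFAS/SF-36 scores, up to all four post-operative surveys for an early stop, and on any later healing status that is not charted.

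The direction and size of bias are unknown. The illustrations of 0.025 SD and 0.075 SD rest wholly on assumed shares and deficits, and equal deficits at equal rates give zero. The documents do not support saying that the clause favours weight-bearing: section 7.3.4 speaks only of a possible minimal increase in risk, and more non-adherence stops under non-weight-bearing is conjecture. Nor do they show that power is compromised. The case for change is that the loss is avoidable, tied to outcome and largely unrecoverable for the surveys, while the remedy is cheap.

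**What to change.** Amend sections 4.4 and 4.5 to state that:

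- adverse events, non-adherence, plan violations and safety decisions lead at most to stopping or changing the assigned weight-bearing regimen, with date and reason recorded;
- missed visits alone do not end participation;
- all remaining Table 1 visits, including their imaging and adverse event assessments, and all AOFAS/SF-36 surveys are still attempted to 24 months and analysed under the assigned arm;
- leaving the study is reserved for withdrawal of consent, or for a documented reason that makes further data collection impossible or inappropriate;
- decisions on care remain with the surgeon.

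Where consent is withdrawn, ask permission for continued chart review of complications and healing, if the consent form does not already do so.

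Under this wording, patients who only stop the regimen have not withdrawn from the study. They therefore do not meet the condition in 4.5.1, and their surveys would be used.

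The cost is a rewording of two sections and possibly one consent sentence. Each affected patient adds at most four questionnaire sessions and some contact attempts, since the visits, examinations and radiographs are already standard care (7.5). Some patients who miss visits will still be unreachable.

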6.2 Secondary Endpoints

The secondary outcome measures are the frequency of complications during the perioperative and post-operative periods, osseous healing as assessed by both clinical and radiographic evaluation, and healing outcomes of soft tissue procedures. These results will be analyzed at the end of the follow-up period.

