6.8 Definition of an Adverse Event

An adverse event is any untoward medical occurrence in a subject who has received an intervention (drug, biologic, or other intervention). The occurrence does not necessarily have to have a causal relationship with the treatment. An AE can therefore be any unfavorable or unintended sign (including an abnormal laboratory finding, for example), symptom, or disease temporally associated with the use of a medicinal product, whether or not considered related to the medicinal product.

All AEs (including serious AEs) will be noted in the study records and on the case report form with a full description including the nature, date and time of onset, determination of non-serious versus serious, intensity (mild, moderate, severe), duration, causality, and outcome of the event.

The risks associated with the study arm, which is immediate weightbearing following foot and ankle surgery include the potential for the following:

- Excessive Pain with weightbearing on the surgical extremity
- Potential wound complications associated with surgical incision sites
- Possible hardware failure
- Possible non-union, mal-union, or delayed union during osseous healing
- Possible non-healing or delayed healing of soft tissue structures

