7.3.2 Risk Assessment

- **7.3.2.1** There is a potential risk for loss of confidentiality in this study which will be minimalized by only the research team accessing the research data and the PHI.
- **7.3.2.2** Unique patient study specific identifiers will be used during data collection.
- **7.3.2.3** All data forms will be maintained in a locked cabinet in the research coordinator's office.
- **7.3.2.4** No PHI will be transferred, shared or stored on personal computers.
- 7.3.2.5 Risk of exposure for X-rays; but the dose involved in general x-rays is minimal.
- **7.3.2.6** There are no increased risks associated with the control arm of the study, which is a traditional non-weight-bearing period of 6 weeks following foot and ankle surgery. The risks associated with the study arm, which is immediate weightbearing following foot and ankle surgery, include potential pain with weightbearing on the surgical extremity; potential wound complications associated with the surgical incision sites; possible hardware failure; possible non-union, mal-union, or delayed union during osseous healing; and/or possible non-healing or delayed healing of soft tissue structures.
- **7.3.2.7** Currently, the post-operative course following foot and ankle surgery is subjective, based on the previous experiences of the surgeon performing the surgery. We do not believe that there is any additional risk associated with the control arm of the study, which is to maintain non-weightbearing for 6 weeks following foot and ankle surgery. All of the potential risks, including pain, non-union, non-healing, infection, wound complications, and others are possible regardless of the post-operative course. Additionally, we believe that the risks associated with immediate weightbearing following foot and ankle surgery are minimal, as there is ample evidence of previous success with immediate weightbearing following certain procedures.
- **7.3.2.8** We will minimize the risk of harm by close follow-up during the post-operative course, utilizing appropriate protective devices during weightbearing following foot and ankle surgery, and thoroughly educating our participants on the warning signs of potential complications, regardless of the study group into which the participant falls.

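### Patients taken off the assigned weight-bearing regimen can be discontinued at the Investigator's discretion and, on the natural reading of 4.5.1, dropped from the final analysis

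*Combined protocol and SAP*

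**What the plan says.** - **Section 4.5** lets a patient be "discontinued from the study at the discretion of the Investigator for lack of adherence to study treatment or visit schedules, or AEs". It continues: "The Investigator may also withdraw subjects who violate the study plan, or to protect the subject for reasons of safety", and adds administrative reasons.
- **Section 4.4** provides for removal from an arm; once someone concludes that "a patient should be withdrawn from one of the two study arms, it will be recorded in the study results". It does not say whether visits continue or how the patient is analysed.
- **Section 4.5.1**: "Subjects who withdraw from the study before the 12 month follow-up visit will not be included in the final analysis of the study".
- **Section 3.1** forms the groups by allocation: patients "will be randomly placed into the study group and control group if they meet all eligibility criteria".
- **Section 6.2**, on complications and on bone and soft-tissue healing: "These results will be analyzed at the end of the follow-up period".
- **The Abstract** (Study Interventions and Measures) gives 6 weeks as the period of non-weight-bearing that is compared with immediate loading in a boot.
- **Section 6.4** names no analysis population. No section states intention-to-treat, a missing-data method or a sensitivity analysis.

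**The concern.** The permitted grounds for discontinuation include adverse events and safety, and these overlap with the outcomes being compared. A study-arm patient who stops bearing weight because of a wound problem can be discontinued, and the chi-square comparison then loses both the patient and the complication. The AOFAS and SF-36 comparisons lose the same patient.

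Safety exits are plausibly more common in the study arm. Section 6.8 lists risks of that arm, beginning with "Excessive Pain with weightbearing on the surgical extremity", and Section 7.3.2.6 says "There are no increased risks associated with the control arm of the study". If so, the exclusion favours immediate weight-bearing on safety, which is half of the purpose stated in Section 2. Non-adherence exits could run the other way, since strict non-weight-bearing can also be broken. The net direction is therefore likely but not certain. Even with equal exits, removing complications makes a real excess harder to detect.

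**Working it through.** **1. The plan's own figure.** For d = 0.40, two-sided 0.05 and 80% power, the noncentral t gives n = 99.08, so 100 per group, with power 0.804. Adding 15 gives 115, and 100/(1 - 15/115) = 115. Section 6.5 reproduces. The 15 are added for loss to follow-up; they replace numbers and do not remove bias from outcome-related exits.

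**2. The textual chain.** Regimen change within 6 weeks → discontinuation or withdrawal permitted (4.5) → before month 12 → not in the final analysis (4.5.1). The first arrow is a choice, not a rule. The last depends on reading withdrawal in 4.5.1 to include the Investigator's action.

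**3. Inputs for an illustration.**
- 100 per arm: the evaluable number in Section 6.5. The plan enrols 115.
- Complications p = 9%: an assumption, close to the 9.5% and 8% that Section 1.2 cites for ankle-fracture series with protected or immediate loading.
- Share s of study-arm complications that exit: 0.10 or 0.25 (assumption).
- Other patients who exit: 2% (assumption).
- Harm scenario: 18% v 9% (assumption, with no source in the documents).
- Test: uncorrected chi-square, two-sided 0.05, by exact enumeration.

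**4. Exits and analysed rates.**

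Exits = p·s + (1 - p)·0.02
- p = 0.09: 0.009 + 0.0182 = 2.7%; 0.0225 + 0.0182 = 4.1%
- p = 0.18: 0.018 + 0.0164 = 3.4%; 0.045 + 0.0164 = 6.1%

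Analysed rate = p(1 - s)/[p(1 - s) + (1 - p)·0.98]
- p = 0.09: 0.081/0.9728 = 8.3%; 0.0675/0.9593 = 7.0%
- p = 0.18: 0.162/0.9656 = 16.8%; 0.135/0.9386 = 14.4%

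With equal exits, the true 9-point excess therefore appears as 16.8 - 8.3 = 8.5 points or 14.4 - 7.0 = 7.4 points.

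**5. Results** (first value s = 0.10, second s = 0.25).

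| Control-arm exits | False finding that the study arm is safer, 9% v 9% | Power to show harm, 18% v 9% |
|---|---|---|
| All patients analysed, both arms | 2.6% | 47% |
| Same as study arm (s, and 2% of others) | 2.5%, 2.5% | 43%, 38% |
| Half (s/2, and 2% of others) | 3.1%, 4.5% | 39%, 28% |
| None | 3.5%, 6.9% | 37%, 22% |

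**6. Primary scores.** With no control exits, shift = exits × gap, where the gap is how far excluded patients score below those who remain (assumed 0.5 to 1 SD). The lowest case is 0.0272 × 0.5 = 0.014 SD. At s = 0.25 and 1 SD it is 0.041 SD. Even at s = 0.50, exits are 0.045 + 0.0182 = 6.3% and the shift is 0.063 SD. Against 0.40 the range is 3% to 16%. Two-sided error at 100 per arm is about 5.1% to 7.3%.

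**The case against.** **Discretion.** Every route in 4.5 is permissive, and nothing equates a change of weight-bearing status with leaving the study. A reader might infer that everyone who comes off the regimen is automatically excluded. The documents do not say so: given Section 3.1, patients who stay would naturally be analysed as assigned. What stands is that an Investigator who knows the patient's weight-bearing status makes the choice, on grounds tied to the outcome.

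**Wording.** Section 4.5 uses discontinued for non-adherence and AEs, while 4.5.1 speaks of subjects who withdraw. Read literally, the AE route may fall outside the exclusion. But 4.5 is headed as withdrawal, its next sentences use withdraw for the Investigator's action on safety and plan violation, and nothing keeps discontinued patients in the analysis. The ambiguity is real and is itself a reason to amend.

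**The complication is not hidden.** A reader might infer that it disappears. It does not: 4.4 keeps unscheduled visits in the study record, 6.8 puts every AE on the case report form, and 6.7 sends AEs to the IRB. The loss is from the formal comparison only.

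**Size.** A reader might take the one-sided extreme, with half of study-arm complications and no control patients exiting. That gives a 20% false-safer rate and 4% power. The documents do not support it. The same discretion covers both arms, and 7.3.2.7 accepts that these complications can occur under either course. Section 1.1 gives 6-8 weeks as average healing time, so many healing failures would surface after the regimen has ended. The 18% rate is unsourced, and 7.3.4 expects only a minimal increase. The complication figures also concern a secondary endpoint; the effect on the primary scores is small. All of this stands and limits the size, but it does not close the route.

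**Conclusion.** The concern holds as a permitted exclusion related to outcome, not as a planned or automatic one. On the natural reading of 4.5.1, patients taken off the regimen can leave the formal comparison of complications, healing and scores. With control complications exiting at half the study-arm rate, the false-safer probability rises from 2.6% to 3.1-4.5%. With equal rates it does not rise, but power to show 18% v 9% falls from 47% to 43-38%. The primary-score shift is at most about 0.06 SD.

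These sizes rest on assumed exit shares, an assumed 9% rate applied to both arms of a mixed surgical population, and 100 rather than 115 patients per arm. Confidence is moderate: the text supports the route, but how often it would be used is unknown. It should be changed, mainly because the trial asks a safety question and the remedy is cheap.

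**What to change.** Added sentences alone would contradict the existing discretion, so the current text must be amended too.

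- **4.5:** delete non-adherence to treatment and AEs as grounds for discontinuing a patient from the study. Limit the plan-violation and safety provisions to stopping the assigned regimen.
- **4.4 and 4.5:** add: *A change from the assigned weight-bearing status, for any reason, is not withdrawal from the study. The patient continues all scheduled visits.*
- **4.5.1 and 6.4.1:** add: *Patients whose weight-bearing status changes are analysed in the arm assigned. The month-12 exclusion does not apply to them.*
- **Optional:** list regimen changes by arm, with date and reason, descriptively.

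Withdrawal of consent is a separate matter and is not covered by this change.

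**Cost:** a few sentences, with no extra patients and no visits beyond the planned schedule. The result will describe the assigned strategy, not sustained loading, with some dilution if patients switch. For example, if 6.3% of the study arm switch and then score like controls, the effect is 0.40 × (1 - 0.063) = 0.375, and power at 100 per arm falls from 0.80 to about 0.75.
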